#### Categorical Analysis

The following categories for change from baseline will be defined:

- Very much better if change from baseline = -4
- Much better if change from baseline = -3
- Better if change from baseline = -2
- Somewhat better if change from baseline = -1
- No changed if change from baseline = 0
- Somewhat worse if change from baseline = 1
- Worse if change from baseline = 2
- Much worse if change from baseline = 3
- Very much worse if change from baseline = 4

In addition, the following simplified categories for change from baseline will be defined:

- Improved (Very much better / Much better / Better / Somewhat better) if change from baseline  $\leq -1$
- No change if change from baseline = 0
- Worse (Very much worse / Much worse / Worse / Somewhat worse) if change from baseline  $\geq 1$

Within-subject change from baseline to Month 7 are summarized as follows:

- Proportion of subjects in each PGI-S category for change from baseline to Month 7.
- Proportion of subjects in each PGI-S simplified category (Improved/No change/Worsen) for change from baseline to Month 7 ( $\leq -1$ , 0,  $\geq 1$ ) by treatment group and pooled.
- Between treatment groups comparison of the proportion of subjects in PGI-S Improved simplified category (i.e., change from baseline to Month 7  $\leq -1$ ) using Cochran-Mantel-Haenszel test stratified by history of MAC lung infection (initial or subsequent).

For the purpose of this analysis, PRO data for subjects with missing data, imputations of change from baseline values will be averaged across 50 available imputations and rounded to the nearest integer to obtain a single value per subject.

### 11.3. Culture Conversion by Month 7

The endpoint of interest is the proportion of subjects achieving culture conversion by Month 7. The reporting will be presented based on the ITT analysis set and will be provided by randomized treatment group.

Converters by Month 7 are subjects who have a negative culture at Month 7, and have achieved culture conversion by one of the following:

- MAC culture negative at Month 6 after adjustment for non-productive sputum, or
- Missing MAC culture at Month 6, and one of the below:
  - Achieved culture conversion (2 consecutive monthly negative sputum cultures), have negative culture after conversion, do not have recurrence after conversion, with at most 1 missing sputum assessment at or before Month 5, or
  - Negative culture at Month 5

Non-converters by Month 7 are subjects who satisfy one of the following criteria:

- Die after randomization, or
- Have a positive MAC culture at Month 6 and/or Month 7 (after adjustment for non-productive)

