Sites are strongly discouraged from performing local mycobacterium sputum cultures for the duration of the study, as this may introduce bias to subject assessments. Sputum may be sent to local laboratories to be cultured for organisms other than mycobacterium.

Microbiological Assessment

Sputum specimens will be cultured in broth media (liquid) in addition to agar media (solid), and will be held for up to 6 weeks. A negative culture result will not be reported until after this time has transpired. All contaminated samples will be retreated and re-cultured once.

Growth of other bacteria due to co-infections (eg, *Pseudomonas aeruginosa*, *M. abscessus*, other NTM) will be reported as applicable. Colony counts of MAC growth will be reported. Isolates of MAC will be identified using a commercial RNA probe (AccuProbe, Gen Probe, Inc., GenoType NTM-DR Ver 1.0, Hain Lifescience) and subsequently identified to species using molecular

methodology (Cousins et al., 1996). Standard antibiotic sensitivity testing using MICs will be routinely performed on mycobacterial isolates (CLSI, 2018a; CLSI, 2018b; Forbes et al., 2008).

The MAC species and genotype at the Screening and/or Baseline sputum specimen will be identified by whole genome sequencing (Illumina Nextseq500TM) in subjects who achieve sputum culture conversion and who subsequently have positive sputum culture(s) (broth or agar); typing by whole genome sequencing will also be conducted.

MAC Culture Assessment Definitions

MAC culture negative	No MAC growth on agar media and broth media in all sputum cultures at a visit.
Non-productive	Prior to culture conversion or post recurrence: visits where subjects were recorded as non-productive are considered MAC culture positive. Post culture conversion: visits where subjects were recorded as non-productive are considered MAC culture negative.
Culture conversion	No MAC growth on agar media and broth media in all sputum cultures at 2 consecutive visits. The date of conversion is defined by the date of the first of 2 consecutive negative cultures.
Recurrence: Relapse	Subsequent to culture conversion, at least 1 MAC positive culture in agar media or positive cultures in broth media in at least 2 consecutive visits. A MAC positive culture is defined as the same species and genome as cultured at Screening/Baseline.

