#### Non-productive sputum assessments

If a subject is unable to produce sputum spontaneously, sputum may be induced. If after induction, a subject is still unable to produce sputum despite reasonable efforts, this will be recorded as non-productive at that timepoint.

A non-productive assessment will be considered culture positive if the assessment occurs prior to culture conversion or post recurrence. A non-productive assessment will be considered culture negative if the assessment occurs post culture conversion.

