### 9.3.1.2.1. Data Handling

For the purpose of the analysis the influence of ICEs ([Section 7.5](#)) and the presence of the missing data on the estimation of culture conversion proportion by Month 6 will be taken into consideration.

Culture conversion by Month 6 will be handled by following rules:

1. Data will be adjusted for non-productive visits
2. A subject who dies after randomization will be considered non-converter by Month 6
3. Retrieved sputum assessments will be used in the analysis, ie, collected after early termination of ALIS/ELC (see [Section 7.4](#) for definition)
4. Subjects with a missing assessment at Month 5 or 6 but not both, will be considered converters by Month 6 if they meet all of the following criteria:
  - achieved culture conversion (2 consecutive monthly negative sputum cultures) at or before Month 5,
  - have negative cultures after conversion with at most 1 missing sputum assessment at or before Month 4,
  - have negative culture at Month 7,
  - do not have recurrence after conversion.

Justification for the rule: The protocol defines culture conversion as no MAC growth on agar media and broth media in all sputum cultures at 2 consecutive visits. Month 6 conversion requires both Months 5 and 6 cultures to be negative for MAC (after non-productivity adjustment); if one of them is missing, culture conversion status cannot be determined. However, in the presence of other post-randomization data, in the instances described above this status may be assigned deterministically, consistent with common clinical practices.

5. Data for subjects who complete 6 months of the randomized treatment however conversion status by Month 6 is not available will be imputed based on the observed status distribution from the subjects who completed 6 months of randomized treatment (ALIS/ELC, AZI, and ETH), have Month 6 conversion

status determined, and were randomized to the same treatment group. This approach is consistent with MAR approach imputation.

6. When retrieved assessments are unavailable or #4 does not provide conversion status by Month 6, the missing Month 6 conversion status will be imputed as follows:
  - For subjects experiencing ICE (other than death), their missing Month 6 conversion status will be imputed based on the retrieved Month 6 conversion distribution from the subjects experiencing ICE (retrievers). MNAR imputation of the data for those subjects experiencing ICE is applied.

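### SAP 11.3 makes a subject a converter by Month 7 on negatives at Months 5 and 7 with Month 6 missing, so two consecutive negative visits need never be shown

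*SAP*

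**What the plan says.** Protocol 8.1 defines culture conversion as "No MAC growth on agar media and broth media in all sputum cultures at 2 consecutive visits". SAP 9.3.1.1 also asks for two consecutive negative visits and places them within the treatment period. It adds that a later positive culture (recurrence) reverses conversion and that a subject may convert again.

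SAP 11.3 adds an endpoint that the protocol does not list: "Converters by Month 7 are subjects who have a negative culture at Month 7, and have achieved culture conversion by one of the following". The first route is a negative Month 6 culture. The second is headed "Missing MAC culture at Month 6, and one of the below" and offers two alternatives joined by *or*:

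- "Achieved culture conversion (2 consecutive monthly negative sputum cultures), have negative culture after conversion, do not have recurrence after conversion, with at most 1" missing assessment at or before Month 5;
- "Negative culture at Month 5", with nothing further required.

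For the Month 6 endpoint, SAP 9.3.1.2.1 states that status cannot be determined when the Month 5 or Month 6 culture is missing. Rule 4 makes an exception for a subject who, among other conditions, "achieved culture conversion (2 consecutive monthly negative sputum cultures) at or before Month 5". Subjects outside rule 4 are multiply imputed.

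**The concern.** The second alternative matters only for subjects who fail the first, chiefly those with no conversion standing at Month 5. It gives them a certain converter status on two isolated negatives separated by a scheduled visit with no culture. That conflicts with the definition in both documents, and SAP 11.3 gives no justification for it, whereas rule 4 of 9.3.1.2.1 is justified at length.

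The status is used in several places:

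- the Month 7 treatment comparison (11.3.1);
- the correlations of PRO change with Month 7 conversion (11.4);
- the cumulative summary in 9.3.4.1, whose denominator is the Month 7 converters. A subject admitted this way can be in that denominator with no date on which conversion occurred;
- the imputation of others. Treatment completers classed this way have a determined status, so they join the reference distribution for subjects in the same arm (11.3.1.1).

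**Working it through.** **Step 1: apply the rules to individual histories.** The inputs are the converter and non-converter rules of SAP 11.3, rule 4 of 9.3.1.2.1, the time-to-conversion definition of 9.3.4.1 and the non-productive rule of 9.3.1.1: "A non-productive assessment will be considered culture positive if the assessment occurs prior to culture conversion or post recurrence". After conversion, a non-productive visit counts as negative. In the table + is positive, - is negative and NP is non-productive.

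| Months 1 to 7 | By Month 7 (11.3) | By Month 6 (9.3.1) | Time to conversion (9.3.4.1) |
|---|---|---|---|
| +,+,+,+,-,missing,- | converter, through Month 5 alternative only | undetermined, imputed | censored |
| +,+,+,+,-,-,- | converter, Month 6 negative | converter | event, Month 5 |
| +,+,-,-,-,missing,- | converter, first alternative | converter, rule 4 | event, Month 3 |
| +,+,+,+,-,NP,- | non-converter (NP counts as positive) | non-converter | censored |
| +,+,-,-,-,NP,- | converter (NP counts as negative) | converter | event, Month 3 |

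Only in the first row do the three analyses disagree.

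**Step 2: how much the alternative admits.** Fix Month 5 negative, Month 6 missing and Month 7 negative. Let each of Months 1 to 4 be negative, positive, non-productive or missing, which gives 4^4 = 256 patterns. Each positive is taken as one that reverses an earlier conversion.

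- All 256 are converters by Month 7.
- 192 qualify only through the Month 5 alternative, so 256 - 192 = 64 qualify through the first.
- 171 of the 192 never show two consecutive negatives.
- If Month 6 is non-productive instead of missing, 180 of the 256 become non-converters. The other 76 do not change, because a conversion is standing.
- So 76 - 64 = 12 of the 192 have a standing conversion and fail the first alternative only for having too many missing cultures. The other 192 - 12 = 180 have none. Of these, 180 - 171 = 9 converted early and then reversed.
- All 192 are undetermined, and so imputed, for the Month 6 endpoint.

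These are counts of patterns, not expected numbers of patients.

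**Step 3: size.** The documents give no rate for a missing Month 6 culture. Take as assumptions:

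- Month 6 missing in 5-20% of subjects;
- of those, 10-20% with no standing conversion but negatives at Months 5 and 7;
- a 50-70% chance that an imputed status would be converter. This borrows the conversion rates used for planning in SAP 4.3.1.

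Share affected: 5% x 10% = 0.5%, up to 20% x 20% = 4%.

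The proper comparison is with imputation, not with non-converter status, so the net shift is the share times (1 - imputation probability): 0.5% x 0.3 = 0.15%, up to 4% x 0.5 = 2%. In an arm of 50, 2% is one subject.

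The 5% and 20% echo the missing-data assumption for QOL-B power in SAP 4.3.1. That assumption also includes 0% and is not a culture rate. The clause needs Months 5 and 7 observed, so dropout does not count. Non-productive visits are not missing, and visits with all samples contaminated count as negative (9.3.1.1). The upper end is therefore generous.

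**The case against.** The strongest defence is that this is an explicit, prespecified rule for bridging one missing culture, in an endpoint that needs its own definition. SAP 9.3.1.1 confines conversion to the treatment period, and Month 7 is off treatment, so even negatives at Months 6 and 7 depart from it. The classification is also wrong only if Month 6 was truly positive between two observed negatives, and rule 4 itself uses a Month 7 negative to help resolve a missing Month 6. The endpoint sits under Other Efficacy Assessments, and SAP 7.2 disclaims inference from any contrast.

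The last point stands and sets the priority. The rest does not rescue the rule. Section 11.3 asks that conversion has been achieved, and its first alternative spells that out as two consecutive monthly negatives. Rule 4 relies on Month 7 only when conversion is already established.

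A reader might also infer that the fault is letting in subjects with an earlier recurrence, for example (-,-,+,+,-,missing,-). The documents do not support that. SAP 9.3.1.1 allows re-conversion, and the Month 6-negative route carries no recurrence condition, so (-,-,+,+,-,-,-) is a valid converter. What is missing in the first sequence is a new pair of consecutive negatives after the reversal.

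**Conclusion.** The concern holds in a limited form. For a subject with a gap at Month 6, no standing conversion, and negatives at Months 5 and 7, SAP 11.3 fixes converter status without the evidence that the plan's own definition requires. It also disagrees with how the plan treats the same history elsewhere. The direction does not depend on the assumed rates, because replacing an imputed status with a certain converter can only raise the conversion count. The size does: about 0.15-2% of subjects on the assumptions above. Priority: minor.

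Three stronger readings go too far:

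- **Conversion is overstated wherever Month 6 is missed.** Subjects with an established, unreversed conversion and at most one earlier gap qualify through the first alternative anyway.
- **The clause alone makes a missed visit score better than a non-productive one.** The difference is real for subjects without a standing conversion, but part of it comes from the protocol's scoring of a pre-conversion non-productive visit as positive. It does not arise for subjects already converted.
- **The treatment comparison is biased toward one arm.** The rule is the same in both arms, and the documents give no arm-specific rate of Month 6 gaps.

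**What to change.** In SAP 11.3, delete the stand-alone Month 5 alternative. Or restrict it to subjects whose most recent conversion (two consecutive monthly negatives, for example Months 4 and 5) still stands at Month 5. Treat the remaining subjects with a missing Month 6 culture as undetermined and impute them under 11.3.1.1.

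The two options differ little. Deletion sends all 192 patterns to imputation. The restriction sends 180 and keeps the 12 with a standing conversion but too many earlier gaps for the first alternative.

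The cost is one wording change and one derivation change. A few more statuses are imputed instead of assigned. Because 11.4 uses only deterministically assigned statuses, the affected subjects drop out of the correlations with Month 7 conversion, even where their PRO change was observed.

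The change narrows the gap between a missed and a non-productive Month 6 visit but does not close it. The missed visit would be imputed, and so be a converter in some imputations, while the pre-conversion non-productive visit would stay a fixed non-converter under the protocol rule. If the sponsor keeps the alternative, 11.3 should justify it and report how many subjects per arm qualify only through it.

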#### 11.3.1. Analysis

Analysis of this endpoint will follow Section [9.3.1.2](#).

### 11.3.1.1. Data Handling

For the purpose of the analysis the influence of ICEs ([Section 7.5](#)) and the presence of the missing data on the estimation of culture conversion proportion by Month 7 will be taken into consideration.

Culture conversion by Month 7 will be handled by following rules:

1. Derive culture conversion by Month 7 using the rules above. Retrieved sputum assessments will be used in the analysis, ie, collected after early termination of ALIS/ELC (see [Section 7.4](#) for definition)
2. Data for subjects who complete 6 months of the randomized treatment however conversion status by Month 7 is not available will be imputed based on the observed status distribution from the subjects who completed 6 months of randomized treatment (ALIS/ELC, AZI, and ETH), have Month 7 conversion status determined, and were randomized to the same treatment group. This approach is consistent with MAR approach imputation.
3. When retrieved assessments are unavailable or #1 does not provide conversion status by Month 7, the missing Month 7 conversion status will be imputed as follows:
  - For subjects experiencing ICE (other than death), their missing Month 7 conversion status will be imputed based on the retrieved Month 7 conversion distribution from the subjects experiencing ICE (retrievers). MNAR imputation of the data for those subjects experiencing ICE is applied.
  - For subjects not experiencing ICE, their missing Month 7 conversion status will be imputed based on the observed status distribution from the subjects who completed 6 months of randomized treatment, have Month 7 conversion status determined, and were randomized to the same treatment group. This approach is consistent with MAR approach imputation.

The ELC treatment group (including retriever) will be used instead if the ICE retriever subgroup is too small to allow imputations as described above. The decision as to which group will be used in the imputation will be determined prior to unblinding at the blinded data review meeting.

Imputation details are included in the [Appendix I](#).

## 11.4. Correlations

Correlations between QOL-B (Respiratory Symptoms Domain), PROMIS F-SF 7a (raw score) (denoted 'PROs' below) and microbiology variables will be investigated. Missing data for this analysis will not be multiply imputed, however all other rules described in [Sections 9.3.1.2](#) and [9.3.2.2](#) that allow deterministically assign missing values will be applied.

- Change from baseline to Month 6 in PROs vs Culture conversion by Month 6
- Change from baseline to Month 7 in PROs vs Culture conversion by Month 6

- Change from baseline to Month 6 in PROs vs Culture conversion by Month 7
- Change from baseline to Month 7 in PROs vs Culture conversion by Month 7

Correlations will be evaluated by treatment group and for overall using point biserial correlation and ANOVA/ANCOVA with response variable of change from baseline in PRO, and independent variables culture conversion status, and treatment (if appropriate). Basic statistics of change from baseline in PRO scores by converter status will also be provided.

In addition, plots of change from baseline PRO mean scores over time will be presented for converters and non-converters.

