### 9.3.2.2.1. Data Handling

For the purpose of the analysis the influence of ICEs and the presence of the missing data on the estimation of change from baseline to Month 7 PRO means will be taken into consideration. The ICEs are defined as post-randomization events leading to early ALIS/ELC therapy termination due to death, ALIS/ELC-related TEAE, use of rescue medication, or lack of efficacy.

Change from baseline to Month 7 will incorporate the following considerations:

1. A subject who dies after randomization will be assigned the worst observed change score in the entire sample as the change from baseline to Month 7
2. Retrieved Month 7 assessments will be used in the analysis, ie, collected after early termination of ALIS/ELC (see [Section 7.4](#) for definition)
3. Data for subjects who complete 6 months of the randomized treatment however their Month 7 PRO is not available will be imputed based on the observed status distribution from the subjects who completed 6 months of randomized treatment (ALIS/ELC, AZI and ETH), have Month 7 available, and were randomized to the same treatment group. This approach is consistent with MAR approach.
4. When retrieved assessments are unavailable the missing change from baseline to Month 7 will be imputed as follows:
  - For subjects experiencing ICEs other than death, their missing Month 7 PRO will be imputed based on the retrieved assessment distribution from those retrievers who experienced ICE and are exposed to an altered treatment regimen after their ICEs. MNAR imputation of the data for those subjects experiencing ICE is applied.

Justification for usage of retrievers' data is included in [Section 9.3.1.2.1](#).

- For subjects not experiencing ICE, their missing Month 7 PRO data will be imputed based on the observed data distribution from the subjects who completed 6 months of randomized therapy (ALIS/ELC, AZI and ETH), have Month 7 PRO data assessment available, and are randomized to the same treatment group. This approach is consistent with Missing-at-Random (MAR) approach.

Imputation details are included in [Appendix I](#).

The ELC treatment group will be used instead if the ICE retriever subgroup is too small to allow imputations as described above. The decision as to which group will be used in the imputation will be determined prior to unblinding at the data review meeting.

The results of the analyses for each imputation will be combined using Rubin's rule.

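### In the Month 7 PRO versus culture conversion correlations, each death enters as a non-converter with the worst PRO change in the sample, which pushes the reported association upward

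*SAP*

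**What the plan says.** SAP 11.4 plans four pairings: PRO change to Month 6 or Month 7, each against conversion by Month 6 or by Month 7. Each is summarised by treatment group and overall, with a point biserial correlation, ANOVA/ANCOVA, basic statistics by converter status, and plots of mean change over time for converters and non-converters.

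On missing data, 11.4 states "Missing data for this analysis will not be multiply imputed", but adds that the remaining rules of 9.3.1.2 and 9.3.2.2 "that allow deterministically assign missing values will be applied". The rules for deaths are:

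- Conversion by Month 6 (SAP 9.3.1.2.1, rule 2): "A subject who dies after randomization will be considered non-converter by Month 6".
- Conversion by Month 7 (SAP 11.3): the list of non-converters opens with "Die after randomization, or".
- PRO (SAP 9.3.2.2.1, rule 1): a subject who dies "will be assigned the worst observed change score in the entire sample as the change from baseline to Month 7". SAP 9.3.3.2 has PROMIS fatigue analysed in a similar way.

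No rule assigns a Month 6 PRO change to a death. Section 11.4 plans no version restricted to observed PRO data. SAP 7.2 makes all results under the SAP descriptive, with nominal p-values.

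**The concern.** Scoring a death as the worst outcome is a defensible composite when two arms are compared, which is its purpose in 9.3.1 and 9.3.2. Section 11.4 asks something else: whether the symptom change that patients report goes along with culture status. A subject who died before Month 7 has no Month 7 questionnaire and so carries no information on that question. Yet the rules place that subject in the non-converter group at the extreme of the PRO distribution. Because death fixes both variables, it builds part of the association into the data.

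The direction is always the same. For QOL-B (higher is better) the assigned value is the lowest change. For PROMIS (lower is better) it is the largest increase, so the sign of r is reversed but the meaning is not. The correlations, the mean differences and the statistics by converter status are all affected. They will be read as evidence on whether the PROs track microbiology, and SAP Table 2 lists the 11.4 correlations among the analyses that may be redone if the PRO scoring changes.

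**Working it through.** **Inputs from the documents (SAP 4.3.1).** N = 100, 50 per arm; conversion 50%, 60% or 70%; polyserial correlation at least 0.40; difference between converters and non-converters 7 points; two-sided 5%; missing data 0%, 5% or 20%.

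**Inputs assumed.** 1 to 3 deaths; about 95 survivors; normally distributed change with SD 11 to 14. The lower SD is implied by the plan (step 2). The upper one is an allowance for larger dispersion.

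**1. The plan's own figure.** A polyserial correlation converts to a point biserial one by r_pb = r_ps × φ(z_p) / √(p(1−p)). At p = 0.5 this is 0.40 × 0.399 / 0.5 = 0.319; at 0.6 it is 0.315 and at 0.7 it is 0.303. Noncentral t power at 50/60/70% conversion is 91.5/90.8/88.4% with no missing data and 84.5/83.6/80.3% with 20% missing. The stated power of at least 80% reproduces.

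**2. Implied SD.** SD = 7 × √(p(1−p)) / r_pb. At p = 0.5 this is 3.5 / 0.319 = 11.0; at p = 0.7 it is 7 × 0.458 / 0.303 = 10.6. So about 11.

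**3. Shift in the converter difference, no true association.** The worst of about 95 values lies about 2.49 SD below the mean. Adding k such values to m = 95 × (1−p) non-converters lowers their mean by k × 2.49 × SD / (m + k).

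- Low end (p = 0.5, m = 47.5, SD 11; 2.49 × 11 = 27.4): 27.4/48.5 = 0.56; 2 × 27.4/49.5 = 1.11; 3 × 27.4/50.5 = 1.63.
- High end (p = 0.7, m = 28.5, SD 14; 2.49 × 14 = 34.9): 34.9/29.5 = 1.18; 2 × 34.9/30.5 = 2.29; 3 × 34.9/31.5 = 3.32.

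Simulation agrees, with high ends of 1.2, 2.4 and 3.4.

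**4. Correlation and nominal rejection, by simulation, no true association, 50-70% conversion.**

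| Deaths | Added difference (points) | Mean r | Nominal 5% rejection |
|---|---|---|---|
| 0 | 0 | 0.00 | 5% |
| 1 | 0.6-1.2 | 0.03-0.04 | about 5% |
| 2 | 1.1-2.4 | 0.05-0.07 | 6-10% |
| 3 | 1.6-3.4 | 0.07-0.10 | 9-16% |

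**5. By arm.** In a 50-subject arm, with the whole-sample worst value as the SAP specifies, 1, 2 or 3 deaths in that arm give a mean r of 0.05-0.07, 0.09-0.13 or 0.12-0.19.

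**6. With the planned association present.** Overall r moves from about 0.30-0.32 to about 0.33 with 1 death and 0.36-0.37 with 3. The added amount is smaller than under no association.

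**The case against.** Several points on the other side have force.

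- **Scope.** The PRO rule is worded for the Month 7 change only. A reader might infer that all four correlations are affected. The text supports this for two: "Change from baseline to Month 7 in PROs vs Culture conversion by Month 6" and "Change from baseline to Month 7 in PROs vs Culture conversion by Month 7". For the Month 6 PRO pairings, and for time points other than Month 7 in the plots, the SAP does not say how deaths are scored. That is a gap in wording, not a demonstrated bias.
- **Size.** The effect grows as the non-converter group shrinks, so figures at 70% conversion alone would overstate it. Hence the full 50-70% range above. One death barely moves the rejection rate, and protocol 1.3.2 describes the patients as having mild disease, so there may be few deaths or none.
- **Status.** A reader might infer an invalid hypothesis test. SAP 7.2 disclaims inference, so no formal error rate is lost. Nominal status does not, however, remove bias from the estimates.
- **Survivorship.** Leaving deaths out conditions on survival. If failure to convert contributes to death, the association among survivors may be too weak. This stands, and it is a reason to keep the assigned-death version as a secondary result.
- **Measured cultures.** A subject who dies late may have real Month 5 and Month 6 cultures, so conversion status is not always invented. The Month 7 PRO change still is.

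**Conclusion.** The point holds for the two pairings that use the Month 7 PRO change. There, SAP 11.4 lets one event set both variables, and the reported association is pushed upward. Overall the push is small with one death and noticeable with three (r up by 0.07-0.10 when the truth is zero); it is larger within an arm. It vanishes with no deaths. These sizes rest on an assumed 1 to 3 deaths and SD 11 to 14, neither of which the documents give.

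A reader might go further and infer that the primary psychometric validation is compromised, since culture conversion is also an anchor there. The documents do not support that. The anchor analysis belongs to the Validation Analysis Plan, which is not among them, so whether the death rules reach it cannot be judged.

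**What to change.** In SAP 11.4:

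1. Base the main analysis on observed PRO changes, including assessments retrieved after ALIS/ELC was stopped. Leave out subjects who died before the PRO visit, and list them.
2. Apply the same rule to the Month 6 PRO pairings and to the converter and non-converter mean plots, where the handling of deaths is now unstated.
3. Show the version with assigned values for deaths as a sensitivity analysis, with the number of deaths.

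Keep the death rules unchanged for the treatment comparisons in 9.3.1 and 9.3.2.

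The cost is a short wording change and one extra set of outputs; no data collection changes. The main correlation becomes conditional on survival and loses a few subjects who have no score at that visit. The sensitivity analysis shows how much that matters.
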